24.4 WEIGHT BEARING GRADE

The categorical variables to be described are, N and (%) and Clopper-Pearson confidence intervals will be shown at 95.0% as well, for the overall population and for subgroups of patients defined according to OI Type Diagnosis (Mild/Non-deforming / Severe / Highly Severe/Progressively deforming / Lethal) as defined in section 15.6 of this document:

- Number of procedures that reached a Full weight-bearing (FWB) from surgery in any visit
- Number of Patients that reached a Full weight-bearing (FWB) from surgery in any visit or procedure

The descriptive statistic (Mean, SD, Median, Q₁, Q₃, Min, Max) will be shown for the following continuous variable, for the overall population and for subgroups of patients defined according to OI Type Diagnosis (Mild/Non-deforming / Severe / Highly Severe/Progressively deforming / Lethal) as defined in section 15.6 of this document:

- Time to Full weight-bearing from surgery (months), per procedure, considered at the first date in which the answer is "Full weight-bearing (FWB)" in "Weight bearing protocol assigned" variables. Calculated as date of the first visit of Full weight-bearing minus date of surgery.

A list with Weight bearing grade variables will be shown.

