5.1 Background Information

Osteogenesis Imperfecta (OI), also called brittle bone disease, is a group of genetic disorders that affect connective tissue due to a lack of type I collagen. The classical Sillence types of OI (types I-IV) with autosomal dominant inheritance comprise about 80-85% of cases and are caused by mutations in the genes that encode type I collagen, COL1A1 and COL1A2. Osteogenesis imperfecta is a very polymorphic condition, apart from the classical autosomal dominant forms, there are also recessive forms, often severe. Forms with hypertrophic calluses (type V DA), and others associated with joint contractures (Bruck's syndrome). Currently, more than twenty affections are identified clinically and by molecular biology studies. The incidence of forms recognizable at birth is 1:10-20,000. The hallmark feature of OI is bone fragility, with susceptibility to fracture from minimal trauma, as well as bone deformity and growth deficiency. Secondary features include dentinogenesis imperfecta (DI), cardiopulmonary complications and, in adult years, hearing loss. The clinical features of OI represent a continuum ranging from perinatal lethality to individuals with severe skeletal deformities, mobility impairments, and very short stature to nearly asymptomatic individuals with a mild predisposition to fractures, normal dentition, normal stature, and normal life span. Fractures can occur in any bone but are most common in the limbs.

Management is ideally done by a multidisciplinary team including specialists in medical management of OI, clinical genetics, orthopedics, endocrinologist, rehabilitation medicine, paediatric dentistry, otology/otolaryngology, and mental health.

Intramedullary nails have an important role for bone stabilization and fracture prevention in patients with OI, who suffer from bone fragility and recurrent fractures. Long bones in the lower limbs of OI patients are especially prone to deformities that develop as a result of bone deformability or from malunion in fractures. Thus, it is important to provide structural support to the weakened bones of these patients, which is better accomplished with the use of intramedullary devices.

The objectives of long bone rodding in OI patients are to:

- Fracture treatment;
- Correct deformity;

- Improve function;
- Restore bone density through functional load bearing.

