13 ANALYSIS POPULATION

- **The Full Analysis Set (FAS) population** will consist of all enrolled patients treated by the means of JTIN application and who didn't oppose to study participation. The FAS population will be used for all the analyses of the study that are presented at subject level.
- **The Full Analysis Implant Set (FAIS) population** will consist of all JTIN applications performed on subjects belonging to the FAS population. The FAIS population will be used for all the analyses of the study that are presented at implant level.

The CRF contains the selection criteria information in the form of a binary variable (Yes/No) for each element described. Patients are considered to belong to the FAS and FAIS populations if they indicate that they meet the selection criteria in the previously mentioned binary variables.

Several of these criteria can be verified with the data recorded in the CRF. The criteria to be verified to define the FAS and FAIS population for the analysis are described below:

INCLUSION CRITERIA

1. *is in pediatric age (> 18 month and < 18 years) at the time of surgery;* The patients' age at surgery must be between 18 months and 18 years.
2. *is skeletally immature;* This criteria cannot be verified with the variables included in the CRF.
3. *has a diagnosis for OI;* The variables "OI Type Diagnosis" and "Treated bone" should be collected in screening visit.
4. *has a regular indication for surgical intervention with JTIN to treat femoral and/or tibial fractures, osteotomies, malunions and non-unions;* The variable "Intended use of JTIN for this case" should be collected in screening visit.
5. *Patient and/or legal representative is duly informed and doesn't oppose to participation.*
This criteria cannot be verified with the variables included in the CRF.

EXCLUSION CRITERIA

1. *has a medical condition that is a contraindication according to the manufacturer's instruction for use;* This criteria cannot be verified with the variables included in the CRF.
2. *has any conditions that in the Investigator's opinion may interfere with the study execution or due to which the patient should not participate for safety reasons;* This criteria cannot be verified with the variables included in the CRF.

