15.7 PRE-OP CLINICAL EXAMINATION AND GILLETTE SCORE BY PROCEDURE

This analysis will be performed on FAIS population.

The categorical variables to be described are, N and (%):

- The patient can stand up? (Yes / No (Non-weight-bearing)), if 'Yes':
 - Pre operative Weight-bearing Protocol (if not prescribed by surgeon, report what is known) (Toe-touch weight-bearing (TTWB) / Partial weight-bearing (PWB)/ Full weight-bearing (FWB)
 - The patient walks? (Yes / No)
- How frequent did the patient reported pain at the affected limb before JTIN application? (Never / Some of the days / About half of the days / Most of the days /Everyday), is not equal to 'Never' VAS Pain Score according to the patient will be described (Mean, SD, Median, Q₁, Q₃, Min, Max)
- Was the pain pharmacologically treated? (Yes / No / unknown)
- Was the Gillet Score performed BEFORE the treatment with JTIN? (Yes / No) is equal to 'Yes' Gillette Functional Assessment Questionnaire result will be described (Mean, SD, Median, Q₁, Q₃, Min, Max)

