24 SECONDARY OBJECTIVE

The secondary objective of the study is to evaluate the clinical safety and performance of JTIN by the three following endpoints, when the MD is used within the scope and according to the manufacturer IFU:

- **Implant survival rate: percentage of not exchanged nails up to 1 year follow-up (safety);**
- **Bone union achievement (performance);**
- **Post-treatment fracture-free survival up to 1 year follow-up (performance)**

This analysis will be performed on FAS/FAIS population.

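### SAP 24.4 reports a full weight-bearing rate that takes no account of pre-operative weight-bearing status, so the rate depends heavily on baseline mobility and no planned table shows within-child change

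*SAP*

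**What the plan says.** SAP 24.4 plans N, percentage and 95% Clopper-Pearson interval for two counts: "Number of procedures that reached a Full weight-bearing (FWB) from surgery in any visit" and "Number of Patients that reached a Full weight-bearing (FWB) from surgery in any visit or procedure". Both are shown "for the overall population and for subgroups of patients defined according to OI Type Diagnosis". Time to FWB runs from surgery to the first visit at which FWB is recorded. A listing of weight-bearing variables is also planned, but its contents are not specified.

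The denominator comes from SAP 24: "This analysis will be performed on FAS/FAIS population". SAP 13 adds: "The Full Analysis Implant Set (FAIS) population will consist of all JTIN applications performed on subjects belonging to the FAS population". Neither the population definitions nor the eligibility criteria (SAP 11 and 12) require that the child can stand.

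Baseline status is available. SAP 15.7 tabulates whether the child can stand and, only if so, the "Pre operative Weight-bearing Protocol (if not prescribed by surgeon, report what is known" (toe-touch, partial or full) and whether the child walks. Protocol 10.2.1 also lists weight-bearing in the baseline examination. Nothing in 24.4 refers back to these items.

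On status within the plan, SAP 24 states: "The secondary objective of the study is to evaluate the clinical safety and performance of JTIN by the three following endpoints". Those three are implant survival, bone union and fracture-free survival. Weight-bearing is not among them, although 24.4 sits under the same heading with the same interval format.

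**The concern.** The count uses an absolute state reached at any time after surgery. In a population with similar mobility before surgery that would be readable. This population is not like that: Protocol 5.1 describes a spectrum from "individuals with severe skeletal deformities, mobility impairments, and very short stature to nearly asymptomatic individuals with a mild predisposition to fractures". The follow-up forms (SAP 19.2, 20.2 and 21.2) even ask why a child cannot stand although the bone has consolidated, so sound healing without standing is foreseen.

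Three consequences follow from the definition:

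- A child unable to stand before surgery and at every later visit is never asked for a grade, so cannot be counted as FWB however well the bone heals.
- A child at FWB before surgery is counted as soon as FWB is recorded again. That is recovery, but it is pooled with new gains.
- A child at FWB at one visit and below it at 1 year remains counted, because one visit is enough.

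At stake is interpretation. A reader could take the percentage as a measure of what the nail achieved, when it also carries the mobility that the children brought to surgery. The split by OI group has the same difficulty to whatever extent mobility differed between groups beforehand.

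**Working it through.** **Planned size.** SAP 9 gives 20 evaluable procedures and 20% non-evaluable. 20 / (1 − 0.20) = 25, as stated. The documents give no planning figure for weight-bearing, so there is none to reproduce.

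**Illustration.** No baseline distribution is given, so the mix below is assumed and varied. Let *a* be the procedures in children who could not stand before surgery, *b* those in children already at FWB, and *c* = 20 − *a* − *b* the rest. Assume that no child in *a* reaches FWB, every child in *b* regains it, and half of *c* reach it. Then:

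- count under 24.4: x = *b* + 0.5*c*
- percentage over all procedures: x / 20
- rate among those able to gain FWB: 0.5*c* / *c* = 50% throughout

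| *a* | *b* | *c* | 24.4 figure (95% Clopper-Pearson) | Among *c* (95% Clopper-Pearson) |
|---|---|---|---|---|
| 10 | 0 | 10 | 5/20 = 25% (8.7–49.1) | 5/10 = 50% (18.7–81.3) |
| 8 | 0 | 12 | 6/20 = 30% (11.9–54.3) | 6/12 = 50% (21.1–78.9) |
| 4 | 4 | 12 | 10/20 = 50% (27.2–72.8) | 6/12 = 50% (21.1–78.9) |
| 0 | 8 | 12 | 14/20 = 70% (45.7–88.1) | 6/12 = 50% (21.1–78.9) |
| 0 | 10 | 10 | 15/20 = 75% (50.9–91.3) | 5/10 = 50% (18.7–81.3) |

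The reported figure moves from 25% to 75% while the rate among those able to gain FWB stays at 50%. In the middle row, 10/20 is made up of 0/4, 6/12 and 4/4, and the single percentage cannot show this.

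**Denominator.** SAP 14 reports both a total percentage and a valid percentage that leaves out missing values. The grade is asked only of children who can stand. If the skipped item is treated as missing, children who never stand leave the valid percentage. The first row becomes 5/(20 − 10) = 50% and the middle row 10/(20 − 4) = 62.5% (35.4–84.8), while the last row stays at 75%. This removes the downward pull of non-standers but not the upward pull of children already at FWB. The natural reading is that a recorded inability to stand is a known status and counts as not reached, but 24.4 does not say so.

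**The case against.** The strongest reply is that the information is already there. Standing, grade and walking are tabulated before surgery (SAP 15.7) and at each later clinical visit (SAP 18.2, 19.2, 20.2 and 21.2), and 24.4 adds a listing. A reader might infer that loss of weight-bearing is concealed. The documents do not support that: a net fall would show in the by-visit distributions, and with about 25 procedures a listing could show individual cases. What remains is narrower. By-visit distributions do not show who moved where, and the listing is not said to include the pre-operative grade.

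Second, the variable is largely the weight-bearing regime assigned after surgery, so returning to FWB is a genuine recovery milestone. A reader might infer that children already at FWB are false successes. That does not follow: the SAP uses neither success nor failure here, and sets no threshold or benchmark for this count. Regained FWB should be shown as maintained, not removed.

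Third, the Gillette questionnaire already compares function before and after surgery (SAP 14 and 25). That is true, but it is a different measure and does not make the FWB percentage interpretable.

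Fourth, the baseline mix is unknown. It would go too far to say that the rate mostly reflects case mix, or that the OI split will show a pre-existing gradient. The documents support only that the rate is strongly sensitive to the mix.

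Finally, status before surgery for an acute fracture may reflect the injury, so a simple shift from baseline would credit healing as improvement. This stands, and the fix has to allow for it.

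**Conclusion.** The point holds as a cheap improvement to a descriptive analysis. SAP 24.4 ignores a baseline that the study collects, its FWB rate depends heavily on pre-operative mobility, and no planned table shows within-child change. The 25% to 75% range rests on 20 procedures, the assumed mixes above, no gain among non-standers, full recovery among those already at FWB, and a 50% rate in the rest. It shows sensitivity and does not predict the result.

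A reader might infer from the placement under the secondary objective that a study endpoint is compromised. It is not: weight-bearing is none of the three secondary endpoints, and no primary or listed secondary result changes.

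**What to change.** In SAP 24.4:

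1. Add a shift table of pre-operative grade (cannot stand / toe-touch / partial / full, from SAP 15.7) against the Visit 6 grade in the same four categories. Give counts improved, maintained and worsened, with regained FWB shown as maintained.
2. Show the table separately for fracture treatment and for the other, elective indications, using the intended-use variable in SAP 15.6, because status before surgery in an acute fracture may reflect the injury.
3. If an FWB rate is kept, give it by pre-operative standing status and state that non-standers stay in the denominator as not reached.
4. Label the section exploratory.

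The cost is one extra table from data already in the eCRF, with no new collection. Cells will be small, all the more so after the split by indication, so report counts instead of leaning on percentages and intervals.

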25 EXPLORATORY OBJECTIVE

Gillette Functional Assessment Questionnaire will be collected before the surgery and then at bone consolidation assessment and at 1 year follow-up.

This analysis will be performed on FAIS population.

The descriptive statistic (Mean, SD, Median, Q₁, Q₃, Min, Max) will be shown for the following continuous variable in the screening and 3er follow up visits per procedure, for the overall population and for subgroups of patients defined according to OI Type Diagnosis (Mild/Non-deforming / Severe / Highly Severe/Progressively deforming / Lethal) as defined in section 15.6 of this document:

- Gillette Functional Assessment Questionnaire result

Comparisons will be performed using paired t-test (parametric) or Wilcoxon (non-parametric) depending on the distribution of the sample.

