7.2 Subjects and Sites Numbers

This study will be conducted only on patients with a regular indication for JTIN as per IFU (no off-label use will be included): the nail is indicated for fractures, osteotomies, malunions and non-unions in femur and tibia in pediatric patients suffering from osteogenesis imperfecta. The JTIN is intended to be used in pediatric patients, older than 18 months.

This study includes only one site (monocentric) located in Paris, France. The site was chosen for this study due to the number of subject devices already implanted, and the wideness of the indications covered by the surgeries. The site was also positively evaluated by sponsor for the appropriate qualification and competency of the investigator and of the staff, and availability of facilities and equipment.

The enrollment objective for this study is of 20 evaluable cases (i.e. procedures, see paragraph "Determination of the Sample Size"). For the purposes of this study, a case is defined as one implanted JTIN nail in one treated bone. Each case can be evaluated and recorded from implantation to the last visit for this study (see "Visits and Assessments Schedule" table and "Procedure" paragraph) or up to implant removal if this happens before the last visit. For each case one eCRF record will be created (see "Subject Identifier" paragraph).

Therefore, a single patient at the clinical site can contribute for more than one case e.g.: a patient can have several JTIN each implanted in a different bone, or can have more JTIN implanted in the same bone but at different times.

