12.3 Determination of the Sample Size

Due to the observational nature of the study, no formal sample size calculation has been done, but a revision of the literature on the complication rates (intended as at least one serious/not serious adverse event certainly or possibly related to the procedure up to 1 year follow-up) has been made. The scientific literature reports that the percentage of procedures which develop at least one serious/not serious adverse event certainly or possibly related to the procedure itself is between 9% and 60%, with a mean of 31%. Assuming a complication rate aligned or better than the mean observed in literature (31%), a sample size of 15 procedures will be sufficient to estimate the adverse event rate with the upper limit of the 95% confidence interval equal or lower than the worst complication rate seen in literature (i.e. 60%).

Starting from this sample size, to also assume that the success rate (intended as proportion of procedures that result in a bone union achieved) is aligned or better than the mean observed in literature (80%), 20 procedures will be needed.

Considering a drop-out or a non-evaluable rate of 20% of the procedures, a total of approximately 25 procedures should be made. Each subject could have from 1 to 4 procedures. Assuming the worst scenario of no more than 1 procedure for subjects, a maximum of 25 subjects needs to be enrolled. Anyway, the enrolment will stop when the total number of the procedures is reached.

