7 EXPLORATORY OBJECTIVE

The Gillette Functional Assessment Questionnaire will be collected, according to hospital standard care, before the surgery Visit 0 (screening)) and at 1 year follow up (Visit 6), to evaluate the changes after treatment.

[figure not shown]
The questionnaire is performed by the investigator the first time (i.e. before the surgery) observing the patient (in presence or eventually via telemedicine), and for the follow-up it can be performed by the investigator by telephone or by email with the parent (or legal representative). The Gillette Functional Assessment Questionnaire is not specific developed for OI patients but it is used in the hospital because no other score is currently available specifically for OI patients. The hospital is aware that other factors for OI patient can interfere with the score.

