 - Please explain your answer and clarify what should be done to fulfil the treatment
 - Is another surgery recommended? (Yes / No), if yes:
 - Why is another surgery recommended?

Note.- Some patients may receive multiple implants during the same surgery. The use of multiple nails can affect surgery time and radiation dose. If multiple implants were used will be determined by identifying cases with the same patient ID and surgery date.

- The number of implants used in the same surgery will be shown (n,%)

In addition, the descriptive statistic (Mean, SD, Median, Q₁, Q₃, Min, Max) will be shown for the following continuous variables based on the number of implants used in the same surgery:

- Radiant dose (Gy). The mean of the values reported for implants with the same date of surgery will be provided.
- Duration of the surgery (hours). The mean of the values reported for implants with the same date of surgery will be provided.

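### SAP 25 tests change in the Gillette score, which rates the child, with one row per nail and no child-level version; same-surgery nails count a child more than once (minor, exploratory)

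*SAP*

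**What the plan says.** SAP 25 assigns the whole Gillette section to the FAIS, which under SAP 13 holds one row per JTIN application. Descriptive statistics "will be shown for the following continuous variable in the screening and 3er follow up visits per procedure". SAP 25 asks for these figures "for the overall population and for subgroups of patients defined according to OI Type Diagnosis". The test follows: "Comparisons will be performed using paired t-test (parametric) or Wilcoxon (non-parametric) depending on the distribution of the sample". SAP 14 sets a two-sided level of 0.05 and adds no clustering term. Protocol 12.2.3 names a paired t-test for the pre-post comparison but does not fix its unit.

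The score belongs to the child. SAP 7 says that the investigator first obtains it by "observing the patient (in presence or eventually via telemedicine"; at follow-up it may be obtained from the parent.

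Several rows per child are expected:

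- Protocol 12.3: "Each subject could have from 1 to 4 procedures".
- Protocol 7.2: a child may have nails in different bones, "or can have more JTIN implanted in the same bone but at different times".
- SAP 16.1: "Some patients may receive multiple implants during the same surgery". It also gives the rule for finding them: "If multiple implants were used will be determined by identifying cases with the same patient ID and surgery date".

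**The concern.** A paired test needs independent pairs. With one row per nail, a child who receives two nails in one operation enters twice, normally with the same screening score and the same 1-year score. The row count then exceeds the number of independent observations, the standard error is too small, and the p-value is too low.

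A child nailed on two occasions contributes two different pairs. They come from the same child, so independence fails there too, though not necessarily in the same direction.

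At stake are the p-value and the apparent sample size for functional change. SAP 14 treats p below 0.05 as statistical significance, and Protocol 14.10 foresees a publication. Unless the number of children is shown, a reader could not tell how many stand behind the test.

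**Working it through.** **Inputs from the documents.** Two-sided level 0.05 (SAP 14). 20 evaluable procedures (Protocol 7.2 and 12.3). One to four procedures per child (Protocol 12.3, SAP 9).

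**The plan's own figures.** 20 / (1 − 0.20) = 25 procedures, as stated. A t-test on 20 independent paired differences has a simulated type I error of 5.0%, the nominal level.

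**Assumptions, because the documents give no figure.** The layout of nails per child, and the within-child correlation of change, rho. Rho = 1 means that the same pair is entered for each nail, the natural case for one surgery. Differences are taken as normal.

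**Step 1. Variance inflation of the mean.** With m nails in a child, the design effect is DE = 1 + rho × (Σm²/Σm − 1).

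- 16 children with one nail and 2 with two: Σm²/Σm = (16 + 8)/20 = 1.2, so DE = 1.20 at rho = 1 and 1.10 at rho = 0.5.
- 10 with one and 5 with two: (10 + 20)/20 = 1.5, so DE = 1.50 and 1.25.
- 10 with two: 40/20 = 2, so DE = 2.00 and 1.50.

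**Step 2. Type I error of the planned t-test on 20 rows (simulation, rounded).**

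| Layout | rho 1 | 0.5 | 0.2 | 0 | −0.2 | −0.5 |
|---|---|---|---|---|---|---|
| 20 children, one nail each | 5% | 5% | 5% | 5% | 5% | 5% |
| 18 children, 2 with two nails | 7% | 6% | 5% | 5% | 4.5% | 4% |
| 15 children, 5 with two nails | 11% | 8% | 6% | 5% | 4% | 2.5% |
| 10 children, all with two nails | 18% | 11% | 7% | 5% | 3% | 1% |

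At rho = 1 the Wilcoxon test gives about 7%, 11% and 17% for the three clustered layouts. Three or four nails per child would raise the figures at positive rho: five children with four nails each give 23% at rho = 0.5 and 39% at rho = 1.

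**Step 3. Exact check of one cell.** With ten children each entered twice, the mean is unchanged and the sum of squares SS doubles. The squared standard error is 2SS/(19 × 20) = SS/190, against SS/(9 × 10) = SS/90 for ten pairs. So t is inflated by √(190/90) = √(19/9) = 1.453. The 20-row critical value is 2.093, and 2.093/1.453 = 1.440. P(|t₉| > 1.440) = 18.4%, which agrees with the table.

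**Step 4. Why staged nails can go the other way.** Suppose that the second baseline is taken at or near the first 1-year score. The changes are then Y2 − Y1 and Y3 − Y2, which share Y2 with opposite signs. With independent visit error of variance σ² and nothing else, the covariance is −σ² and each variance is 2σ², so rho = −0.5. A stable tendency of some children to improve more than others pushes rho upward. The documents do not show which effect dominates.

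**Step 5. One pair per child.** Simulated type I error returns to 5.0% with 18, 15 or 10 children.

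**The case against.** The strongest objection concerns direction. A reader might infer that the test overstates the evidence whenever a child has more than one nail. The documents do not support that. It holds for same-surgery nails that carry the same score pair. For staged nails the correlation may be zero or negative, and the test is then at or below 5%. This objection stands, and the point is limited accordingly.

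A second objection is that SAP 25 follows the SAP's usual pattern. This stands in part. Child-level versions exist for demographics (SAP 15.3 beside 15.4) and for most counts (adverse events, device deficiencies, union, fracture, full weight bearing). Continuous outcomes, such as the times to consolidation, fracture and full weight bearing, are per procedure only. Gillette differs from them because it is the only one with a named hypothesis test. Nor does SAP 25 breach SAP 13, which assigns FAS or FAIS by the level at which an analysis is presented.

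Third, the per-procedure wording sits in the sentence on the descriptive table. However, the FAIS assignment covers the whole section and no other unit is given for the test.

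Fourth, one might infer that small OI subgroups will be tested in the same way. SAP 25 attaches the subgroups to the descriptive statistics, and the comparison sentence does not mention them. No error rate is claimed for them here.

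Finally, the endpoint is exploratory, Protocol 12.1 describes such testing as descriptive, and both documents caution that other factors can interfere with the score. This stands and keeps the point minor.

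**Conclusion.** The gap is real and minor. As written, the Gillette test uses one row per nail for a score that rates the child, and it counts a child more than once when several nails are placed in one surgery.

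For positive within-child correlation (0.2 to 1), the type I error on 20 rows is about 5–7% with 2 two-nail children, 6–11% with 5, and 7–18% if all ten children have two nails. These figures rest on assumed layouts and correlations, because the documents give neither these nor the split between same-surgery and staged nails. With one nail per child or zero correlation there is no inflation; with negative correlation the test is conservative.

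A reader might take this as a threat to the study's conclusions. It is not: no decision rule uses the Gillette p-value, and no primary or secondary result depends on it.

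**What to change.** Change SAP 25 only, before database lock:

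1. Run the comparison on the FAS with one before/after pair per child, taken from the child's first enrolled surgery.
2. Collapse nails that share patient ID and surgery date, using the SAP 16.1 rule, and query any differing scores among them. Link staged surgeries through the eCRF field that refers to the first ID (Protocol 7.4.2).
3. If a later surgery is used because the first lacks a complete pair, say so and list those children.
4. Report the numbers of children and of nails. The per-nail descriptive table can stay.
5. State whether OI subgroups are tested. If they are, apply the same one-pair rule.

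The cost is SAP wording and light programming. No new data and no protocol change are needed, since Protocol 12.2.3 leaves the unit open. The downside is fewer pairs: 18, 15 or 10 instead of 20 in the layouts above. The change detectable with 80% power becomes 0.70, 0.78 or 1.00 SD, against a nominal 0.66 SD for 20 independent pairs. Later pairs from staged nails do not enter the test.
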